#### **Appendix 2. ECOG Performance Status**

#### Score Definition

- 0 Fully active, able to carry on all pre-disease activities without restriction.
- 1 Restricted in physically strenuous activity but ambulatory and able to carry out work of a light or sedentary nature, eg, light house work or office work.
- 2 Ambulatory and capable of all selfcare but unable to carry out any work activities. Up and about more than 50% of waking hours.
- 3 Capable of only limited selfcare, confined to bed or chair more than 50% of waking hours.
- 4 Completely disabled. Cannot carry on any selfcare. Totally confined to bed or chair.
- 5 Dead.

# Appendix 3. Child-Pugh Classification (CPC) of Liver Dysfunction

CPC score is calculated from the sum of the points for each CPC criteria:

CPC Classification	Level of dysfunction	Score
А	Mild	5-6
В	Moderate	7-9
С	Severe	≥10

Assessment parameters	Assigned score for observed findings			
CPC Criteria	1	2	3	
Encephalopathy grade (see table below)	0	1 or 2	3 or 4	
Ascites	Absent	Asymptomatic	Requiring intervention	
Serum total bilirubin, mg/dL	<2	2 to 3	>3	
Serum albumin, g/dL	>3.5	2.8 to 3.5	<2.8	
Prothrombin time, sec prolonged	<4	4 to 6	>6	

Encephalopathy	Definition	
Grade	(electroencephalogram [EEG] required for Gr. 2,3,4)	
0	Normal consciousness, personality, neurological exam	
1	Restless, sleep disturbed, irritable/agitated, tremor, impaired	
	handwriting	
2	Lethargic, time-disoriented, inappropriate, asterixis, ataxia, slow	
	triphasic waves on EEG	
3	Somnolent, stuporous, place-disoriented, hyperactive reflexes,	
	rigidity, slower waves on EEG	
4	Unrousable coma, no personality/behavior, decerebrate, slow 2-3 cps	
	delta activity on EEG	

# Appendix 4. Bone Marrow Reserve in Adults

# *Adapted from R.E. ELLIS*: The Distribution of Active Bone Marrow in the Adult, Phy. Med. Biol. 5, 255-258, 1961

SITE		MARROW wt. (g)	FRACTION RED MARROW AGE 40	RED MARROW wt. (g) AGE 40	% TOTAL RED MARROW	
CRANIUM AND MANDIBLE	Head: Cranium Mandible	165.8 16.4	0.75 0.75	136.6 124.3 12.3	13.1	13.1
HUMERI, SCAPULAE, CLAVICLES	Upper Limb Girdle: 2 Humerus, head & neck 2 Scapulae 2 Clavicles	26.5 67.4 21.6	0.75 0.75 0.75	86.7 20.0 50.5 16.2	8.3	8.3
STERNUM AND RIBS	Sternum Ribs: 1 pair 2 3 4 5 6 7 8 9 10 11 12	39.0 10.2 12.6 16.0 18.6 23.8 23.6 25.0 24.0 21.2 16.0 11.2 4.6	0.6 All 0.4	23.4 82.6 4.1 5.0 6.4 7.4 9.5 9.4 10.0 9.6 8.5 6.4 4.5 1.8	2.3	10.2
PELVIC BONES	Sacrum 2 os coxae	194.0 310.6	0.75 0.75	145.6 233.0	13.9 22.3	36.2
FEMUR	2 Femoral head and neck	53.0	0.75	40.0		3.8

# **Marrow Distribution of the Adult**

SITE		MARROW wt. (g)	FRACTION RED MARROW AGE 40	RED MARROW wt. (g) AGE 40	% TOTA RED MA	
VERTEBRAE	Vertebrae (Cervical): 1 2 3 4 5 6 7 Vertebrae (Thoracic): 1 pair 2 3 4 5 6 7 8 9 10 11 12	6.6         8.4         5.7         5.8         7.0         8.5	All 0.75	35.8         5.0         6.3         4.1         4.3         4.4         5.3         6.4         147.9         8.1         8.8         8.5         9.1         10.1         11.5         12.1         13.9         14.8         15.9         16.3         18.8	3.4	28.4
	Vertebrae (Lumbar): 1 pair 2 3 4 5	27.8 29.1 31.8 32.1 31.4	All 0.75	114.1 20.8 21.8 23.8 24.1 23.6	10.9	
TOTAL		1497.7		1045.7	100.0	100.0

# Marrow Distribution of the Adult (cont'd)

# **Appendix 5. Medications with Potential PR Prolongation Effect**

Please note that the drugs listed below are examples and this is not intended to be an all-inclusive listing (from Nada A, et al. Am Heart J 2013;165:489-500).

Electrophysiologic Effects of Select Drugs on PR Interval Based on Product Labeling							
Drug	Action	Indications					
Affecting AV nodal conduction (PR interval							
Adenosine	Adenosine receptor	PSVT					
Amiodarone	Cardiac ion channels	Antiarrhythmics					
Disopyramide							
Encainide							
Flecainide							
Moricizine							
Propafenone							
Verapamil							
Arsenic trioxide	Multiple actions	Acute promyelocytic Leukemia					
Atazanavir	HIV-protease inhibitors	Antiretroviral inhibitor					
Lopinavir/Ritonavir							
Saquinavir							
Digoxin	Multiple actions	Congestive heart failure					
Dolasetron	5HT3 receptor antagonist	Antiemetic					
Fingolimod	S1P receptor modulator	Multiple sclerosis					
Lacosamide	Not fully characterized	Partial-onset seizures					
Pregabalin	Not fully characterized	Neuropathic pain					
Mefloquine	Plasmodicidal effects	Antimalarial					
	using the PDR3D database for PR inte						
	block", "AV conduction delay", or "hea						
	basis on descriptions of PR prolongatio	n/AVB contained with Warning or					
Precautions sections of drug l							
PSVT, Paroxysmal supravent	tricular tachycardia.						

#### Appendix 6. RECIST Version 1.1

The determination of antitumor efficacy during this study will be based on objective tumor assessments made according to the RECIST system of unidimensional evaluation.

#### **Measurability of Tumor Lesions**

At baseline, individual tumor lesions will be categorized by the Investigator as either measurable or non-measurable by the RECIST criteria as described below.

#### Measurable:

Tumor lesion: Must be accurately measured in at least one dimension (longest diameter in the plane of measurement is to be recorded) with a minimum size of:

- 10 mm by CT scan (CT scan slice thickness no greater than 5 mm);
- 10 mm caliper measurement by clinical exam (lesions which cannot be accurately measured with calipers should be recorded as non-measurable).

Malignant lymph nodes: To be considered pathologically enlarged and measurable, a lymph node must be  $\geq 15$  mm in short axis when assessed by CT scan (CT scan slice thickness recommended to be no greater than 5 mm). At baseline and in follow-up, only the short axis will be measured and followed.

**Non-Measurable:** All other lesions, including small lesions (longest diameter <10 mm or pathological lymph nodes with  $\geq$ 10 mm to <15 mm short axis) as well as truly non-measurable lesions. Lesions considered truly non-measurable include: leptomeningeal disease, ascites, pleural or pericardial effusion, inflammatory breast disease, lymphangitic involvement of skin, or lung, abdominal masses/abdominal organomegaly identified by physical exam that is not measurable by reproducible imaging techniques.

NOTE: If measurable disease is restricted to a solitary lesion, its neoplastic nature should be confirmed by cytology/histology.

#### **Recording Tumor Measurements**

All measurable lesions up to a maximum of 2 lesions per organ and 5 lesions in total representative of all involved organs should be identified as **target lesions** and measured and recorded at baseline and at the stipulated intervals during treatment. Target lesions should be selected on the basis of their size (lesion with the longest diameters) and their suitability for accurate repetitive measurements (either by imaging techniques or clinically).

The longest diameter will be recorded for each target lesion. The sum of the longest diameter for all target lesions will be calculated and recorded as the baseline sum longest diameter to be used as reference to further characterize the objective tumor response of the measurable dimension of the disease during treatment. All measurements should be performed using a caliper or ruler and should be recorded in metric notation in centimeters.

All other lesions (or sites of disease) should be identified as **non-target lesions** and should also be recorded at baseline. Measurements are not required and these lesions should be followed as "present" or "absent."

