#### 4.1. Inclusion Criteria

Patients must meet all of the following inclusion criteria to be eligible for enrollment in the study:

- 1. Females and/or male patients age  $\geq 18$  who have the capability to consent for themselves.
- 2. Histologically or cytologically confirmed solid malignancy or lymphoma that is metastatic or unresectable, and for which standard curative or palliative measures do not exist, or are no longer effective.

In case of hepatocellular carcinoma, the diagnosis should be based on at least one of the following:

- a. The presence of at least one lesion, measuring ≥2 cm, with characteristic arterial enhancement and venous washout in the setting of liver cirrhosis and/or hepatitis B or C infection;
- b. The presence of liver lesion(s) (as defined in a.) with alpha-fetoprotein (AFP) ≥400 ng/mL;
- c. Tissue confirmation.
- 3. Biliary obstruction for whom a biliary drain or stent has been placed are eligible, provided that the drain or stent have been in place for at least 10 days prior to the first dose of lorlatinib, and the liver function has stabilized as defined by 2 measurements at least 5 days apart that put the patient in the same hepatic dysfunction stratum as defined in Section 3.1.
- 4. Presence of gliomas and brain metastases only if neurologically stable and treated without ongoing requirement for corticosteroids for at least 2 weeks prior to the first lorlatinib dose.
- 5. Eastern Cooperative Oncology Group (ECOG) Performance Status (PS) 0, 1 or 2.

- 6. Adequate Bone Marrow Function, including:
  - d. Absolute Neutrophil Count (ANC)  $\geq 1,500/\text{mm}^3$  or  $\geq 1.5 \times 10^9/\text{L}$ ;
  - e. Platelets  $\geq 50,000/\text{mm}^3 \text{ or } \geq 50 \text{ x } 10^9/\text{L};$
  - f. Hemoglobin  $\geq 8 \text{ g/dL}$ .
- 7. Adequate Pancreatic Function, including:
  - g. Serum total amylase ≤2. 0 x upper limit of normal (ULN) without symptom of acute or chronic pancreatitis;
  - h. Serum lipase  $\leq 2.0$  x ULN without symptom of acute or chronic pancreatitis.
- 8. Adequate Renal Function, including:

eGFR  $\geq$ 90 mL/min as calculated using the Modification of Diet in Renal Disease (MDRD) equation as follows: *eGFR* (*mL/min/1.73* m^2) = 175 × (Scr,std)-1.154 × (Age)-0.203 × (0.742 if female) × (1.212 if African American).

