# **Definitions of Tumor Response**

# **Target Lesions**

- Complete response (CR) is defined as the disappearance of all target lesions. Any pathological lymph nodes (whether target or non-target) must have reduction in short axis to <10 mm.
- **Partial response (PR)** is defined as a ≥30% decrease in the sum of the longest dimensions of the target lesions taking as a reference the baseline sum longest dimensions.
- **Progressive disease (PD)** is defined as a ≥20% increase in the sum of the longest dimensions of the target lesions taking as a reference the smallest sum of the longest dimensions recorded since the treatment started, or the appearance of one or more new lesions. In addition to the relative increase of 20%, the sum must also demonstrate an absolute increase of at least 5 mm.
- Stable disease (SD) is defined as neither sufficient shrinkage to qualify for PR nor sufficient increase to qualify for PD taking as a reference the smallest sum of the longest dimensions since the treatment started.

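### RECIST appendix: nodes are to be followed by short axis only, yet PR, SD and PD rest on a sum of longest diameters with no nodal exception

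*Protocol*

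**What the plan says.** All of the following stands in the current Protocol Appendix 6 unless another place is named.

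- **Measurability.** Non-nodal lesions and nodes are treated separately. A node is measurable from 15 "mm in short axis when assessed by CT scan", and for nodes "At baseline and in follow-up, only the short axis will be measured and followed".
- **Choice of target lesions.** "All measurable lesions up to a maximum of 2 lesions per organ and 5 lesions in total representative of all involved organs" become target lesions. Nodes are not excluded.
- **Recording.** "The longest diameter will be recorded for each target lesion". Then: "The sum of the longest diameter for all target lesions will be calculated and recorded as the baseline sum longest diameter".
- **PR.** A reduction of at least 30%, worded as a "decrease in the sum of the longest dimensions of the target lesions taking as a reference the baseline sum longest dimensions".
- **PD and SD.** PD needs a rise of at least 20% and at least 5 mm in the same sum over its smallest value, or a new lesion. SD is what meets neither PR nor PD.
- **CR.** All target lesions must disappear, and "Any pathological lymph nodes (whether target or non-target) must have reduction in short axis to <10 mm". The sum is not used.

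Protocol 4.1, criterion 2, admits "Histologically or cytologically confirmed solid malignancy or lymphoma that is metastatic or unresectable", so nodal target disease is possible. Protocol 7.3 names Appendix 6 as the response criteria. SAP 5.2.1 points to RECIST in its own Appendix 1, but that appendix covers relative dose. SAP 5.2.1 also takes the investigator's best response as recorded, without deriving it by program.

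**The concern.** For a nodal target lesion, the recording section asks for a dimension that the measurability section says is not collected. A site cannot follow both. Nothing in Appendix 6 says that the short axis enters the sum, and the SAP applies no central rule that would bring differing site readings into line.

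The investigator's call feeds two named secondary endpoints. ORR counts PR and CR, so a PR/SD difference changes it. DR runs from the first documented response to progression or death, so both a PR/SD and an SD/PD difference can change it. Protocol 3.1 and 5.4 also tie the length of treatment to disease progression, so the call matters beyond the tables.

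**Working it through.** There is no planned figure to reproduce here. The check applies the appendix's own thresholds twice to the same lesion, once with each axis in the sum.

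**Inputs from Appendix 6.** PR: (current − baseline)/baseline ≤ −30%. PD: (current − nadir)/nadir ≥ +20% and current − nadir ≥ 5 mm. Otherwise SD.

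**Assumed inputs.** The node sizes, written longest × short axis in mm, are illustrations; the documents give none. Each case has a single nodal target lesion unless stated, no new lesion and no change elsewhere. A PR is taken to be confirmed at the repeat scan.

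| Change | Short axis in the sum | Longest diameter in the sum |
|---|---|---|
| Baseline 30 × 16 to 24 × 11 | (11 − 16)/16 = −31.3%: PR | (24 − 30)/30 = −20.0%: SD |
| Baseline 36 × 20 to 25 × 16 | (16 − 20)/20 = −20.0%: SD | (25 − 36)/36 = −30.6%: PR |
| Nadir 20 × 15 to 26 × 17 | (17 − 15)/15 = +13.3%, +2 mm: SD | (26 − 20)/20 = +30.0%, +6 mm: PD |
| Nadir 40 × 20 to 44 × 25 | (25 − 20)/20 = +25.0%, +5 mm: PD | (44 − 40)/40 = +10.0%, +4 mm: SD |
| Nadir 40 × 20 to 44 × 27, plus a stable 10 mm non-nodal target lesion | (37 − 30)/30 = +23.3%, +7 mm: PD | (54 − 50)/50 = +8.0%, +4 mm: SD |

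The disagreement goes in both directions and does not need a node-only patient.

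**Size for ORR.** Protocol 9.5.1 takes ORR relative to the response-evaluable set: treated patients with an adequate baseline tumor assessment. Its size per group is not stated. Two bounding assumptions:

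- *Enrollment in proportion to the PK targets, all response-evaluable.* About 76 enrolled for 38 PK-evaluable (Protocol 3.1 and 9.2) is a ratio of 76/38 = 2. Groups of 8 become 16, and the severe group of 6 becomes 12. One patient is 1/16 = 6.3 points or 1/12 = 8.3 points.
- *Only the PK-evaluable numbers are response-evaluable.* One patient is 1/8 = 12.5 points or 1/6 = 16.7 points.

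For all groups together, with at most 76 patients, one patient is 1/76 = 1.3 points. Exact 95% intervals give the scale: 0/16 is 0% (0 to 20.6%) and 1/16 is 6.3% (0.2 to 30.2%); 0/8 is 0% (0 to 36.9%) and 1/8 is 12.5% (0.3 to 52.7%).

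**The case against.** The best reply is that the specific rule governs the general one. The measurability section attaches the longest diameter to non-nodal lesions and gives nodes their own rule. If only the short axis is collected, it is the only nodal value that can enter a sum, and the later wording is loose drafting. RECIST v1.1 is also named as the standard throughout, and nothing shows that sites would actually split. This reading is plausible, and the fix adopts it. But the appendix does not state it, and the recording rule covers each target lesion and the sum covers all of them. A site that follows that text literally will use the longest diameter.

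The reply is right about weight. The primary endpoints are steady-state AUC24 and Cmax, SAP 4.1 plans no formal hypothesis testing, and SAP 5.2.2 expects few responders.

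A reader might infer more than the documents support:

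- *That the axis conflict also turns CR into SD.* Take an assumed node of 25 × 16 going to 18 × 9 mm. It meets the nodal limit of under 10 mm, while its longest diameter falls by 28%. But CR does not use the sum, so changing the axis in the sum does not alter whether CR is met. The doubt there is between disappearance and the 10 mm limit inside the CR definition, which is a separate point.
- *That a shift of 12.5 to 16.7 points is the expected size.* Those figures rest on PK-evaluable counts, and ORR uses a different set. They are an upper case for undivided groups. Splitting Group C by dose, as SAP 5 provides, could make a stratum smaller still.
- *That an SD/PD difference moves ORR.* By itself it does not.
- *That nodal target lesions will be common, or that readings will differ between hepatic groups.* No tumor mix or nodal frequency is given, and nothing links sites to hepatic groups. Admitting lymphoma shows only that the case can arise.

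**Conclusion.** The contradiction is real and stands in the current text. Read literally, Appendix 6 lets the same nodal change be PR or SD, or SD or PD, depending on which sentence a site follows, and the SAP does not settle it. The reach is limited to ORR, DR and the call of progression, in patients whose nodal target disease lies near a threshold. The primary PK analysis is untouched.

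Each reclassified responder moves a group's ORR by about 6 to 8 points under proportional enrollment, and by up to 12.5 to 16.7 points if only 6 to 8 per group are response-evaluable. Either shift is small beside the exact intervals. How many patients would be affected cannot be estimated from the documents. The wording should be corrected because a stated endpoint rule cannot be carried out as written, not because the study's main conclusion depends on it.

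**What to change.** Reconcile the recording and response-definition sections of Appendix 6 with its nodal rule. Wherever the sum of longest diameters or longest dimensions appears, replace it with: *sum of diameters (longest diameter for non-nodal target lesions, short axis for nodal target lesions)*. Apply this to the baseline sum, the smallest sum on study, PR, SD and PD, and make the same distinction in the sentence on what is recorded for each target lesion.

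As a separate clarification, say in the CR definition that disappearance applies to non-nodal target lesions and that the short-axis limit of under 10 mm applies to nodes.

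The cost is a wording change in one appendix, a note to sites, and a re-read of existing scans where nodal target lesions have already been recorded. Protocol 7.3 already requires the images to be available. No new procedure is needed.

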#### **Techniques for Assessing Measurable Disease**

The same method of assessment and the same technique should be used to characterize each identified and reported lesion at screening and during follow-up. Imaging-based evaluation is preferred to evaluation by clinical (physical) examination when both methods have been used to assess the antitumor effect of a treatment.

# **Definitions of Tumor Response**

# **Target Lesions**

- Complete response (CR) is defined as the disappearance of all target lesions. Any pathological lymph nodes (whether target or non-target) must have reduction in short axis to <10 mm.
- **Partial response (PR)** is defined as a ≥30% decrease in the sum of the longest dimensions of the target lesions taking as a reference the baseline sum longest dimensions.
- **Progressive disease (PD)** is defined as a ≥20% increase in the sum of the longest dimensions of the target lesions taking as a reference the smallest sum of the longest dimensions recorded since the treatment started, or the appearance of one or more new lesions. In addition to the relative increase of 20%, the sum must also demonstrate an absolute increase of at least 5 mm.
- Stable disease (SD) is defined as neither sufficient shrinkage to qualify for PR nor sufficient increase to qualify for PD taking as a reference the smallest sum of the longest dimensions since the treatment started.

#### Non-Target Lesions

- **Complete response (CR)** is defined as the disappearance of all non-target lesions. All lymph nodes must be non-pathological in size (<10 mm short axis).
- Non-CR/Non-PD is defined as a persistence of  $\geq 1$  non-target lesions.

- **Progressive disease (PD)** is defined as unequivocal progression of existing non-target lesions, or the appearance of ≥1 new lesion.
- The cytological confirmation of the neoplastic origin of any effusion that appears or worsens during treatment when the measurable tumor has met criteria for response or stable disease is mandatory to differentiate between response or stable disease and progressive disease.

#### **Confirmation of Tumor Response**

To be assigned a status of PR or CR, changes in tumor measurements in patients with responding tumors must be confirmed by repeat studies that should be performed  $\geq 4$  weeks after the criteria for response are first met. In the case of SD, follow-up measurements must have met the SD criteria at least once after study entry at a minimum interval of 8 weeks.

#### **Determination of Tumor Response by the RECIST Criteria**

When both target and non-target lesions are present, individual assessments will be recorded separately. Determination of tumor response at each assessment is summarized in the following table.

Target Lesions 	Non-Target Lesions 	New Lesions 	Tumor Response
CR	CR	No	CR
CR	Non-CR/non-PD	No	PR
CR	Not evaluated	No	PR
PR	Non-PD or not all evaluated	No	PR
SD	Non-PD or not all evaluated	No	SD
PD	Any response	Yes or No	PD
Any response	PD	Yes or No	PD
Any response	Any response	Yes	PD

#### **Response Evaluation Criteria in Solid Tumors**

 Measurable lesions only.

 May include measurable lesions not followed as target lesions or non-measurable lesions.

 Measurable or non-measurable lesions.

#### **Determination of Best Overall Response**

The best overall response is the best response recorded from the start of the treatment until disease progression/recurrence (taking as reference for progressive disease the smallest measurements recorded since the treatment started). For CR and PR, the patient's best response assignment will depend on the achievement of both measurement and confirmation criteria. In the case of SD, follow-up measurements must have met the SD criteria at least once after study entry at a minimum interval of 8 weeks.

NOTE: Patients with a global deterioration of health status requiring discontinuation of treatment without objective evidence of disease progression at that time should be reported as "symptomatic deterioration". Every effort should be made to document the objective progression even after discontinuation of treatment. It should also be noted that a tumor marker increase does not constitute adequate objective evidence of tumor progression. However, such a tumor marker increase should prompt a repeat radiographic evaluation to document whether or not objective tumor progression has occurred.

In some circumstances, it may be difficult to distinguish residual disease from normal tissue. When the evaluation of complete response depends upon this determination, it is recommended that the residual lesion be investigated by fine needle aspirate or biopsy before confirming the complete response status.
